9.3. ADVERSE EVENTS

Adverse events will be collected and recorded from the time a subject signs the informed consent form (ICF) to the last scheduled contact. And new serious adverse events (SAE) reported by the subject to the investigator that occur after the last scheduled contact, and are determined by the investigator to be reasonably associated with the use of the investigational product, should be reported to the sponsor or designated personnel. This may include SAEs that are captured on follow-up telephone

contact or at any other time point after the defined study period (i.e., up to last scheduled contact). The investigator should follow SAEs identified after the last scheduled contact until the events are resolved, or the subject is lost to follow-up. The investigator should continue to report any significant follow-up information to the sponsor until the event has been resolved. This study requires that subjects be actively monitored for SAEs for at least 4 weeks after the last treatment.

For all AEs, preferred AE terms and system organ class (SOC) will be coded using terminology from the Medical Dictionary for Regulatory Activities (MedDRA), version 19.0.

A treatment-emergent adverse event (TEAE) is defined as an AE that begins after the first administration of double-blind study medication or existing AEs that worsen after the first dose of double-blind study medication. All reported AEs will be listed, but only TEAEs will be summarized in tables.

Drug-related AEs will be considered those to be possibly, probably and definitely related to bexagliflozin administration based on the investigators assessment.

Unless otherwise specified, AEs will be summarized by SOC and PT, with SOCs presented in the standard international order and PTs within SOCs presented in descending order of subject incidence.

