9.8.1 Adverse Events

AEs will be mapped to preferred term and body system using the Medical Dictionary for Regulatory Activities (MedDRA) dictionary. AEs that begin at or after the first administration of double-blind study medication or existing AEs that worsen in severity after the first dose of double-blind study medication are considered treatment emergent AEs (TEAE). The number and percentage of subjects reporting TEAEs will be summarized for each treatment group by MedDRA system organ class and preferred term. Further summaries by severity, and by relationship to study treatment will also be provided. Drug-related adverse events will be considered those to be at least possibly related to the study treatments based on the investigators assessment.

The number and percentage of subjects reporting serious AEs, and the number and percentage of subjects reporting AEs leading to treatment discontinuation will also be summarized for each treatment group by MedDRA system organ class and preferred term.

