6.2.3. Study Day

Study Day is the number of days starting from the first administration of double-blind study drug, which is counted as Study Day 1. If the assessment date is after the date of the first double-blind medication, the study day is calculated as date of assessment - date of the first dose administration+1. If the assessment date is prior to the date of the first double-blind medication, the study day is calculated as date of assessment - date of the first dose administration.

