9.3.1. Derived Data

AE onset day is calculated as (date of AE start - date of double-blind first dose + 1). The onset day will be missing if the start date is missing or partially missing.

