9.3.2. Data Summarization

AE summary tables are listed below:

- An overall summary of the number and percentage of subjects reporting any TEAEs, serious TEAEs, treatment-related TEAEs, serious TEAEs, serious treatment-related TEAE, any TEAEs leading to treatment discontinuation, any TEAEs leading to subject discontinuation and TEAEs leading to death.
- TEAEs overall and by SOC and PT
- TEAEs by severity, overall and by SOC and PT
- Serious TEAEs, overall and by system organ class and preferred term

- TEAEs by relationship to study treatment, overall and by system organ class and preferred term
- TEAEs leading to treatment discontinuation, overall and by SOC and PT
- TEAEs leading to study discontinuation, overall and by SOC and PT
- Most common TEAEs. Most common TEAEs are defined as TEAEs that occur in > 5% of the subjects in either of the treatment groups.
- Serious treatment-related TEAEs, overall and by SOC and PT.

For summary tables, subjects having more than 1 event with the same PT will be counted once for that term. Subjects having more than 1 event with the same SOC will be counted once for each event and once for that SOC. For tabulations by severity, only a subject's most severe event within the category (e.g. overall, SOC, PT) will be counted; similarly, for tabulations by relationship, only a subject's most related event within a category will be counted. The denominator for percentages will be the number of subjects in the Safety Analysis Set for the given treatment group (i.e., the N's for the columns).

Listings will be provided for all AEs and the following subsets:

- All TEAEs at least possibly related to study treatment
- Serious AEs
- AEs leading to treatment discontinuation
- AEs leading to death.

Additional information will be collected for diabetic ketoacidosis (DKA). These data will be listed.

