9.3.3.2. Hypoglycemic Events

Hypoglycemic event categories include:

Category	Description
Severe	Assistance required and blood glucose ≤ 70 mg/dL or no value available but responded to glucose treatment
Documented Symptomatic	Blood glucose ≤ 70 mg/dL and typical symptoms of hypoglycemia
Asymptomatic	Blood glucose ≤ 70 mg/dL and no typical symptoms of hypoglycemia
Probable Symptomatic	Typical symptoms of hypoglycemia and no value available but responded to glucose treatment
Relative	Typical symptoms of hypoglycemia and blood glucose > 70 mg/dL

While each event meeting the criteria above will be entered into the hypoglycemia log, only critical (severe) hypoglycemia, documented symptomatic hypoglycemia, asymptomatic hypoglycemia, and probable hypoglycemia will be entered as AEs.

The number and percentage will be summarized by treatment for:

- Each category of hypoglycemic events;
- Any severe or documented hypoglycemic events.

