Table 14.3.1.2	Treatment-Emergent Adverse Events by System Organ Class and Preferred Term (Safety Analysis Set)
Table 14.3.1.3	Treatment-Emergent Adverse Events by System Organ Class, Preferred Term and Maximum Severity (Safety Analysis Set)
Table 14.3.1.4	Treatment-Emergent Adverse Events by System Organ Class, Preferred Term and Relationship to Study Drug (Safety Analysis Set)
Table 14.3.1.5	Most Common Treatment-Emergent Adverse Events by System Organ Class and Preferred Term (Safety Analysis Set)
Table 14.3.1.6	Treatment-Emergent Serious Adverse Events by System Organ Class and Preferred Term (Safety Analysis Set)
Table 14.3.1.7	Serious Treatment-Emergent Treatment Related Adverse Events by System Organ Class, Preferred Term and Relationship to Study Drug (Safety Analysis Set)
Table 14.3.1.8	Summary of Treatment Emergent Adverse Events Leading to Treatment Discontinuation by System Organ Class and Preferred Term (Safety Analysis Set)
Table 14.3.1.9	Summary of Treatment Emergent Adverse Events Leading to Study Discontinuation by System Organ Class and Preferred Term (Safety Analysis Set)
Table 14.3.1.10	Summary of Treatment Emergent Adverse Events of Interest (Safety Analysis Set)
Table 14.3.1.11	Summary of Treatment Emergent Hypoglycemia Events (Safety Analysis Set)
Table 14.3.1.12	Summary of Revascularization and Amputations (Safety Analysis Set)
Table 14.3.2.1	List of Serious Adverse Events (Safety Analysis Set)
Table 14.3.2.2	List of Adverse Events Leading to Treatment Discontinuation (Safety Analysis Set)
Table 14.3.2.3	List of Adverse Events Leading to Death (Safety Analysis Set)
Table 14.3.4.1	Summary of Hematology: Results and Change from Baseline by Visit (Safety Analysis Set)
Table 14.3.4.2	Shift in Clinical Laboratory Values: Hematology (Safety Analysis Set)
Table 14.3.4.3	Summary of Serum Chemistry: Results and Change from Baseline by Visit (Safety Analysis Set)

Number	Title
Table 14.3.4.4	Shift in Clinical Laboratory Values: Serum Chemistry (Safety Analysis Set)
Table 14.3.4.5	Summary of Urinalysis: Results and Change from Baseline by Visit - Continuous Variables (Safety Analysis Set)
Table 14.3.4.6	Summary of Urinalysis Results by Visit - Categorical Variables (Safety Analysis Set)
Table 14.3.4.7	Shift in Clinical Laboratory Values: Urinalysis (Safety Analysis Set)
Table 14.3.5	Summary of Vital Signs: Results and Change from Baseline by Visit (Safety Analysis Set)

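### The SAP narrows the protocol's onset rule for treatment-emergent events from *at or after* to *after* the first dose, does not declare the change, and gives no rule for events dated on the first-dose day

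*SAP*

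**What the plan says.** Protocol 9.8.1 treats as treatment-emergent "AEs that begin at or after the first administration of double-blind study medication". In SAP 9.3 a treatment-emergent event "is defined as an AE that begins after the first administration of double-blind study medication". Both documents add existing events that worsen after the first dose.

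The SAP then makes the definition decide what is tabulated: "All reported AEs will be listed, but only TEAEs will be summarized in tables". The displays in SAP 9.3.2 start with "An overall summary of the number and percentage of subjects reporting any TEAEs", and SAP 9.3.3.1 summarizes special-interest events as TEAEs too. For hypoglycemia, SAP 9.3.3.2 says that, besides severe and documented symptomatic events, "asymptomatic hypoglycemia, and probable hypoglycemia will be entered as AEs". Table 14.3.1.11 in the SAP's index is titled "Summary of Treatment Emergent Hypoglycemia Events (Safety Analysis Set".

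On timing, SAP 6.2.2 takes the first-dose date from the CRF. SAP 9.3.1 says "AE onset day is calculated as (date of AE start - date of double-blind first dose + 1", closing the bracket there. SAP 6.2.3 numbers study days from the first administration, "which is counted as Study Day 1".

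SAP 13, on changes from the protocol, covers model covariates, the retrieved-dropout primary analysis and the removal of LOCF. It does not mention the TEAE definition.

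**The concern.** The two documents give different onset rules for the flag that controls the AE summary tables, and the SAP does not declare the difference. The only events on which the rules can part are those of the first-dose day. An acute reaction to a first dose would carry that date. Hypersensitivity reactions and hypoglycemia are both named as events of special interest. For rare acute events one or two cases may be the whole signal, so whether they reach the summary tables should not depend on how one programmer reads one word.

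**Working it through.** No stated figure of the plan is at issue, so the check compares wording and then applies date logic.

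**1. Resolution of the data.** The SAP's onset derivation uses two calendar dates and no clock time. The hypoglycemia diary in Protocol 6.14.11 does record the time of symptoms, but the SAP names no time of first dose to compare it with.

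**2. Both rules on the date scale.** Onset day = AE start date − first-dose date + 1, as in SAP 9.3.1.

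| AE start date | Onset day | *After*, coded as date > first-dose date | *At or after*, coded as date ≥ first-dose date |
|---|---|---|---|
| Day before first dose | −1 + 1 = 0 | not a TEAE | not a TEAE |
| Day of first dose | 0 + 1 = 1 | not a TEAE | TEAE |
| Day after first dose | 1 + 1 = 2 | TEAE | TEAE |

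The rules differ for onset day 1 and nowhere else.

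**3. Is the strict coding plausible?** Usage elsewhere in the SAP points both ways.
- SAP 7.5.1 puts a medication that stops on the first-dose date on the prior side.
- SAP 6.2.1 lets baseline include a value obtained on, as well as before, the first dose.
- The earliest post-baseline windows in SAP 6.4 open on Day 2.
- SAP 6.2.3, on the other hand, numbers the first-dose day as Study Day 1, which places it on treatment.

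Where the SAP wants the first-dose date included in a comparison, it says so. A programmer could therefore code *after* as a strict inequality, and another who follows the protocol would not.

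**4. Displays affected under the strict coding.**
- Would lose onset-day-1 events: Tables 14.3.1.1 to 14.3.1.10, and 14.3.1.11 by its title and the general sentence in SAP 9.3. The text of SAP 9.3.3.2 does not itself say treatment-emergent.
- Would keep them: the AE listings; Tables 14.3.2.1 to 14.3.2.3 for serious events, events leading to treatment discontinuation and deaths; and the key secondary hypoglycemia analysis (SAP 8.2.3, Tables 14.2.4.1 to 14.2.4.4) for severe or documented symptomatic events, since that endpoint is not defined through TEAEs.

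**5. Size.** Day 1 is one of 96 × 7 = 672 scheduled treatment days, and 1/672 = 0.15%. That fraction says little about acute first-dose reactions, which cluster on that day. The documents give no same-day rate, so a rate r is assumed. With 210 subjects per arm, the expected number affected is 210 × r, and the chance of at least one in an arm is 1 − (1 − r)^210.

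| Assumed r | Expected subjects per arm | Chance of at least one in an arm |
|---|---|---|
| 0.1% | 0.21 | 19% |
| 0.5% | 1.05 | 65% |
| 1% | 2.1 | 88% |
| 2% | 4.2 | 99% |

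**The case against.** The strongest reply is that the SAP text excludes nothing of importance. It ties the definition to the first administration, a moment in time, and not to the first-dose date. A reaction two hours after the dose begins after that administration and is a TEAE as written. On that reading the two definitions differ only for an event that starts at the same instant as the dose, and any event the dose caused must start later. SAP 9.3.1 derives an onset-day variable and says nothing about TEAE status. The table shells and appendix are attachments outside the available text, so the actual programming of the flag cannot be seen.

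This reply stands as a reading of the sentence. It rules out a stronger claim that a reader might infer, namely that the SAP excludes first-dose reactions, or that they vanish from every table. The documents do not support that. The loss needs a date-level coding that the SAP does not state, and even then it is limited to the treatment-emergent summaries. Under Protocol 6.14.11 severe hypoglycemia is recorded as an SAE, so it would stay visible in Table 14.3.2.1 as well as in the key secondary analysis.

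The reply does not remove the undeclared difference in wording. It also does not supply the missing rule: with dates alone, the literal reading cannot be applied to an event dated on the first-dose day.

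A second objection concerns the remedy. AEs are assessed at Visit V6 (Protocol 7.3.1), when double-blind drug is first dispensed, so a rule based on dates can admit events that began before the dose. This is true and is the price of the fix.

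**Conclusion.** The mismatch is exact and undeclared, and the SAP leaves first-dose-day events without a rule at the date resolution it uses. Whether any event is lost depends on coding the definition as a strict comparison of dates, which is plausible but not stated. If it is coded that way, the effect is confined to onset-day-1 events in Tables 14.3.1.1 to 14.3.1.11, with 14.3.1.11 included on the strength of its title.

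The numbers are probably small: about 0.2 to 4.2 subjects per arm over an assumed range of 0.1% to 2%, which has no source in the documents. The primary analysis and the key secondary analyses are untouched. The point is minor. It concerns an analysis definition and not clinical management, and it merits correction because the correction is cheap.

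**What to change.** In SAP 9.3, restore the protocol's *at or after* for onset. Add that an AE with a start date equal to the date of first double-blind dose is treatment-emergent unless a recorded time shows onset before that dose. Leave the clause on worsening events tied to *after* the first dose, as it is in both documents. If the narrower onset wording is intended, declare it in SAP 13 with a reason, and still state how events dated on the first-dose day are flagged.

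The cost is one or two sentences in the SAP and one condition in the derivation of the flag. Only onset-day-1 events can change status. The downside is that a few events that began earlier on the same day, before the dose, may be counted, which errs in the conservative direction for safety.

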Serious and Unexpected Suspected Adverse Reaction (SUSAR): The sponsor must report in an Investigational New Drug (IND) safety report any suspected adverse reaction to study treatment (including active comparators) that is both serious and unexpected (21 CFR

312.32(c)(1)(i)). Before submitting an IND safety report, the sponsor needs to ensure that the event meets all three of the definitions:

- Suspected adverse reaction
- Serious
- Unexpected

Severity: AEs will be graded on a 3-point scale and reported as indicated in the CRF. The intensity of an adverse experience is defined as follows:

- 1 = Mild: event is medically significant but produces no disruption to daily activity;
- 2 = Moderate: event is medically significant and reduces or affects normal daily activity;
- 3 = Severe: event is medically significant and results in inability to work or perform normal daily activity.

Investigational Product Causality: An assignment will be made by the investigator based on the circumstances of the event and its analysis. Cases with causal relationship classified as possible, probable or definite are defined as related. Cases with causal relationship categorized as not likely or unrelated are defined as not related. Relationship of an AE to dosing will be assessed as follows:

Definite: The event responds to withdrawal of the investigational product (dechallenge), and recurs with rechallenge by administration of the investigational product.

Probable: There is a reasonable causal relationship between the investigational product and the AE. The event responds to dechallenge. Rechallenge is not required.

Possible: There is a reasonable causal relationship between the investigational product and the AE. Dechallenge is lacking or dechallenge response is unclear.

Not Likely: There is a temporal relationship to investigational product administration, but there is not a reasonable causal relationship between the investigational product and the event.

Unrelated: There is not a temporal or causal relationship to investigational product administration.

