3.10. ADMINISTRATION OF STUDY MEDICATION

The following investigational products will be used for oral administration:

- Bexagliflozin tablets, 20 mg: tablets containing 20 mg of bexagliflozin
- Bexagliflozin tablets, placebo: tablets containing no bexagliflozin

Active comparator will be:

- Glimepiride capsules, 2 mg: capsules containing 2 mg of glimepiride
- Glimepiride capsules, 4 mg: capsules containing 4 mg of glimepiride
- Glimepiride capsules, 6 mg: capsules containing 6 mg of glimepiride
- Glimepiride capsules, placebo: capsules containing no glimepiride

Bexagliflozin tablets, 20 mg or placebo, should be taken with 250 mL of water in the morning prior to eating or drinking. On the day of scheduled clinic visits when there is

fasting and blood is to be drawn, administration of bexagliflozin should be delayed until after blood is drawn and taken in the clinic or at home prior to the first meal with 250 mL of water.

Glimepiride capsules, 2, 4 or 6 mg or placebo, should be taken once daily with the first meal. On the day of scheduled clinic visits when there is fasting and blood is to be drawn, administration of glimepiride shall be withheld until the first meal.

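### SAP 9.3 defines a drug-related adverse event by relation to bexagliflozin alone, contrary to protocol 9.8.1 and to the SAP's own output specifications

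*SAP*

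**What the plan says.** SAP 9.3 contains the SAP's only definition of relatedness: "Drug-related AEs will be considered those to be possibly, probably and definitely related to bexagliflozin administration based on the investigators assessment".

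Protocol 9.8.1 defines the same term differently: "Drug-related adverse events will be considered those to be at least possibly related to the study treatments based on the investigators assessment". Protocol 6.14.1 fixes the grades that count: "Cases with causal relationship classified as possible, probable or definite are defined as related". It describes the investigator's judgement against a single object. For the possible and probable grades, for example: "There is a reasonable causal relationship between the investigational product and the AE". The same section, on expedited reporting, treats active comparators as part of study treatment.

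The outputs that use relatedness are specified in SAP 9.3.2. They include "TEAEs by relationship to study treatment, overall and by system organ class and preferred term" and a listing of "All TEAEs at least possibly related to study treatment". The overall summary also has rows for treatment-related and serious treatment-related events. In SAP section 17, Tables 14.3.1.4 and 14.3.1.7 are titled by relationship to study drug. No output is specified by relationship to bexagliflozin.

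SAP section 13, on changes from the protocol, covers the model covariates, the retrieved-dropout analysis and the removal of LOCF. It does not mention the definition of drug-related.

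**The concern.** Every subject takes a tablet and a capsule, and one of the two is placebo. The investigator judges causality without knowing which. A definition tied to the tablet's drug is not neutral between the arms: it counts causality for the test drug and leaves out causality for the comparator. SAP 3.4 makes comparison of adverse events between the arms a safety objective, and protocol 3.2.3 acknowledges that sulfonylureas carry a known risk of hypoglycemia. Attribution to the capsule is therefore to be expected.

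The exposure is confined to outputs that use relatedness: the related rows of Table 14.3.1.1, and Tables 14.3.1.4 and 14.3.1.7. If the SAP 9.3 wording were programmed literally, related events could be undercounted there, mainly in the glimepiride arm. To a lesser extent this could also happen in the bexagliflozin arm, through events attributed to the placebo capsule. Protocol 9.1 says that the SAP will be the final plan, so the protocol's wider definition does not prevail automatically.

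**Working it through.** The documents give no figure to reproduce. The check compares the texts and then asks what follows under each way of recording causality.

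**Step 1: the definitions side by side**

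| Place | Grades counted | Related to what |
|---|---|---|
| Protocol 6.14.1 | possible, probable, definite | the investigational product |
| Protocol 9.8.1 | at least possible | the study treatments (plural) |
| SAP 9.3 | possible, probable, definite | bexagliflozin |
| SAP 9.3.2, table and listing | by relationship; at least possible | study treatment |
| SAP 17, Tables 14.3.1.4 and 14.3.1.7 | by relationship | study drug |

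The grades agree throughout. Only the object of the judgement differs, and SAP 9.3 is the only place that names bexagliflozin.

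**Step 2: does the term investigational product settle it?**

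It does not.
- Protocol 5.1.1 uses the heading for bexagliflozin, and 5.1.2 puts glimepiride under active comparator. SAP 3.10 makes the same split, with a separate list introduced by "Active comparator will be".
- Protocol 6.13, on dispensing investigational product, includes glimepiride as 6.13.2. Protocol 5.1.2 also calls the glimepiride capsules investigational drugs.

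The term can therefore mean one product or both.

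**Step 3: the consequence in each case**

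| How causality is recorded or read | SAP 9.3 applied literally | SAP 9.3.2 wording applied |
|---|---|---|
| One rating for blinded study drug as a whole | Nothing can be separated by product, so nothing is lost | Nothing is lost |
| One rating, read as bexagliflozin only | Capsule-only events are not counted | Still not counted, because the rating itself leaves them out |
| One rating per product | Capsule-only events are not counted | Counted |

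Neither document says which row applies.

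**Step 4: size**

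Within one arm, let p be the proportion of subjects with at least one event related to either product. Let s be the share of those subjects whose related events are all attributed to the capsule alone. The related-event percentage then falls by p × s. In the first row of Step 3, s = 0 and the loss is 0. The upper limit is s = 1, where the loss equals p. The documents give neither p nor s, so no narrower range can be supported.

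**Step 5: what does not use relatedness**

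- The key secondary hypoglycemia endpoint and its sensitivity analysis (SAP 8.2.3 and 8.2.4).
- The summary of hypoglycemia by category (SAP 9.3.3.2, Table 14.3.1.11).
- Adverse events of special interest, including rates per 100 patient-years (SAP 9.3.3.1).
- The tables of all TEAEs, severity, all serious TEAEs and discontinuation.

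The definition does not affect any of these.

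**The case against.** The strongest reply is that no loss of events has been shown. Events can be separated by product only if causality is recorded per product, and protocol 6.14.1 describes one scale. On the natural blinded reading, a single rating covers whatever the subject was taking. The output specifications in SAP 9.3.2 already speak of study treatment, and the related-event listing there all but repeats the protocol's threshold. The wording in 9.3 may simply be left over from another plan: SAP 8.1.1 also mentions a placebo group in a trial without a placebo arm, and week 24 values for a week 60 endpoint. The CRF and the table shells, which would settle the matter, are not in the documents.

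Most of this stands. A reader might infer that events attributed to glimepiride do drop out and that the safety comparison between the arms is distorted. The documents do not support that. They show no per-product rating, and hypoglycemia, the most obvious candidate, is compared without any relatedness filter. They also offer no basis for a figure in percentage points.

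The reply does not rescue the sentence itself. Leftover or not, it is the only rule a programmer will find behind the labels in SAP 9.3.2, and it contradicts both those labels and the protocol. A single rating is not clearly safe either, because the plan's own headings allow investigational product to be read as bexagliflozin alone.

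**Conclusion.** Wrong as written; minor severity. SAP 9.3 limits drug-related to bexagliflozin, in conflict with protocol 9.8.1, SAP 9.3.2 and the titles of Tables 14.3.1.4 and 14.3.1.7, and section 13 does not declare the change. This rests on the text alone.

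The effect on results is conditional. An undercount, mainly in the glimepiride arm, arises if the definition is applied literally to per-product ratings, or if investigators take the single rating to concern bexagliflozin only. With one rating for blinded study drug as a whole, it is zero. Any effect is limited to the relatedness rows of Table 14.3.1.1 and to Tables 14.3.1.4 and 14.3.1.7, which are descriptive. No efficacy conclusion, hypoglycemia analysis or unfiltered safety table depends on it.

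**What to change.** In SAP 9.3, replace the relation to bexagliflozin with the protocol 9.8.1 definition, and state that it covers either blinded product (bexagliflozin or its placebo, glimepiride or its placebo). Add a sentence saying how the CRF records causality. If it is recorded per product, count an event as related when either rating qualifies; attribution by product can be shown as a supplementary column.

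The cost is a sentence or two in the SAP and a check that the programming of the three tables follows it. No new data are needed, and no efficacy analysis changes. Because the change restores the protocol definition, section 13 needs no entry for it.
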